#### **6.4.6.3 Bleeding assessment**

For all bleeding events the investigator will complete information on the eCRF specific to that bleeding event. For all bleeding events (excluding minimal) relevant additional source information will be compiled into a “Bleeding Package” as described in the Endpoint Reporting Manual for Investigators. The package will be sent to the ICAC for central adjudication.

Bleeding event data will be collected in sufficient detail so that categorisation according to other previously published definitions (eg, TIMI, ISTH, GUSTO, STEEPLE, BARC) will be possible. The ICAC will adjudicate and evaluate bleeding events (excluding minimal) according to the above bleeding definitions.

Bleeding endpoints will be assessed by investigator according to PLATO definitions.

#### **6.4.6.4 Bleeding associated with procedures**

Information regarding the relationship of any bleed to coronary (CABG, PCI or coronary angiography) will be recorded on the eCRF. The ICAC will adjudicate if bleeding associated with procedures is related to that procedure or not.

Bleeding associated with a procedure should be reported as an AE if the amount of bleeding exceeds the quantity expected by the investigator for this corresponding procedure.

#### **6.4.7 Laboratory safety assessment**

Blood samples for determination of clinical chemistry, haematology will be taken at the times indicated in the Study Plan (see on Table 1). No fasting is required.

The following laboratory variables will be measured and analyzed locally for all patients:

##### **6.4.7.1 Haematology and Clinical chemistry**

---

Clinical chemistry (S denotes serum)	Haematology (B denotes whole blood)
S-Creatinine	B-Haemoglobin
S-Alkaline phosphatase	B-Haematocrit
S-Aspartate aminotransferase (AST)	B-Platelets
S-Alanine aminotransferase (ALT)	B-White blood cells
S-Total Bilirubin	B-White blood cells (differential)
	B-Haemoglobin A1c (only diabetics)

---

##### **6.4.7.2 Myocardial necrosis biomarkers**

The myocardial necrosis biomarkers (Troponin I or T) are required to document the index event and should be obtained to evaluate any recurrences of cardiac ischaemia. They will be analyzed locally for all patients to and will be collected at the following time points:

- In the Cath Lab (V2-pre PCI)
- And then at 8, 16 and 24 hours after PCI

Blood samples for Troponin measurement will also be collected whenever a patient is experiencing chest pain or cardiac event. The result will be part of the endpoint package for ICAC.

All local laboratory results and relevant reference ranges must be stored in the patient's medical record as source documentation.

For blood volume see Section 7.1

#### **6.4.8 Physical examination**

A physical examination will be performed by medically qualified individuals. The targeted examination should include general appearance, cardiovascular, respiratory, abdomen and neurological evaluations. Results will be recorded as an overall normal or abnormal with a listing of abnormalities.

Please refer to the Study Plan (Table 1) in Section 3.1.

#### **Killip classification will be assessed as:**

Killip class I: Absence of rales over the lung fields and absence of an S3

Killip class II: Rales over 50% or less of the lung fields or the presence of an S3

Killip class III: Rales over more than 50% of the lung fields

Killip class IV: Cardiogenic shock: signs include hypotension (systolic pressure of 90 mmHg or less) and evidence of peripheral vasoconstriction such as oliguria, cyanosis and diaphoresis.

#### **6.4.9 Vital signs**

Heart rate, systolic blood pressure (BP) and diastolic BP will be assessed after the patient has been at rest for 5 minutes.

Please refer to the Study Plan in Section 3.1

## 7. BIOLOGICAL SAMPLING PROCEDURES

### 7.1 Volume of blood

The total volume of blood that will be drawn from each patient in this study is as follows:

**Table 2** Volume of blood to be drawn from each patient

For patients participating in the sub study presented in appendix D: an additional volume of 40 ml will be drawn (see details in appendix D).

Assessment		Sample volume (mL)	No. of samples	Total volume (mL)
Baseline (V2)	Clinical chemistry	5	1	5
	Haematology	2	1	2
	Troponin I or T	2	1	2
Safety	Clinical chemistry	5	3	15
	Haematology	2	3	6
	Troponin I or T	2	5	10
Total			14	40

### 7.2 Handling, storage and destruction of biological samples

The samples will be used up or disposed of after analyses.

### 7.3 Labelling and shipment of biohazard samples

Not Applicable.

For patients participating in the sub study presented in appendix D, see details in appendix D.

### 7.4 Chain of custody of biological samples

A full chain of custody is maintained for all samples throughout their lifecycle according to the local practice.

For patients participating in the sub study presented in appendix D, see details in appendix D and E.

## **8. ETHICAL AND REGULATORY REQUIREMENTS**

### **8.1 Ethical conduct of the study**

The study will be performed in accordance with ethical principles that have their origin in the Declaration of Helsinki and are consistent with ICH/Good Clinical Practice, applicable regulatory requirements and the AstraZeneca policy on Bioethics and Human Biological Samples.

### **8.2 Patient data protection**

The Informed Consent Form will incorporate (or, in some cases, be accompanied by a separate document incorporating) wording that complies with relevant data protection and privacy legislation.

### **8.3 Ethics and regulatory review**

An Ethics Committee should approve the final study protocol, including the final version of the Informed Consent Form and any other written information and/or materials to be provided to the patients. Distribution of these documents to the applicable Ethics Committee will either be done by the investigator or by AstraZeneca, according to the national guidelines. Investigator will ensure distribution of these documents to the study site staff.

The opinion of the Ethics Committee should be given in writing. The investigator should submit the written approval to AstraZeneca before enrolment of any patient into the study.

AstraZeneca should approve any modifications to the Informed Consent Form that are needed to meet local requirements.

If required by local regulations, the protocol should be re-approved by the Ethics Committee annually.

Before randomisation of any patient into the study, the final study protocol, including the final version of the Informed Consent Forms, is approved by the national regulatory authority or a notification to the national regulatory authority is done, according to local regulations.

AstraZeneca will handle the distribution of any of these documents to the national regulatory authorities.

AstraZeneca will provide Regulatory Authorities, Ethics Committees and Principal Investigators with safety updates/reports according to local requirements, including SUSARs (Suspected Unexpected Serious Adverse Reactions), where relevant.

## **8.4 Informed consent**

The ambulance medical personnel or paramedics personnel (according to local regulations), will:

- Ensure each patient is given full and adequate oral and written information about the nature, purpose, possible risk and benefit of the study,
- Ensure each patient is notified that they are free to discontinue from the study at any time,
- Ensure that each patient is given the opportunity to ask questions.

### **In emergency situation:**

In emergency situation it might be impossible to take enough time to provide informed consent by the full version of the Informed Consent Form. If locally approved by the Ethics Committee and Regulatory Authorities (if appropriate), a short form of the Informed Consent Form will be provided. It can be used in pre-hospital settings to collect consent of the patient or its legally acceptable representative to confirm that the ambulance personnel/physician (according to local law) has discussed the study with the patient.

When prior consent of the patient or its legally acceptable representative is not possible, the patient may be randomised if the ambulance personnel/physician (according to local law) has attested on the Informed Consent Form that the information about the study has been discussed with the patient.

In all cases, the patient's signature or that of the patient's legally acceptable representative will be obtained on the full version of the Informed Consent Form. If only the short form of the Informed Consent Form is signed then the full Informed Consent Form will be obtained before first dose intake of active ticagrelor 90 mg tablet to document the patient's willingness to continue. If a patient is unable to read and sign due to critical condition, the full Informed Consent Form will be signed as soon as the clinical situation allows it.

If the patient or legally acceptable representative subsequently refuses to complete the consent process, the patient is terminated from the trial, following full discussion with the patient regarding the risks associated with trial termination, and no additional data from the patient is collected. The data collected up to the refusal will be used.

The Principal Investigator (s) at each centre will:

- Ensure that each patient has signed the full Informed Consent Form prior to be given the first dose of active ticagrelor (90 mg tablet)
- Ensure all original, signed Informed Consent Form(s) are stored in the Investigator's Study File,

- Ensure a copy of the signed Informed Consent Form(s) is given to the patient,

## **8.5 Changes to the protocol and informed consent form**

Study procedures will not be changed without the mutual agreement of the International coordinating Investigator and AstraZeneca.

If there are any substantial changes to the study protocol, then these changes will be documented in a study protocol amendment and where required in a new version of the study protocol (Revised Clinical Study Protocol).

The amendment is to be approved by the relevant Ethics Committee and if applicable, also the national regulatory authority approval, before implementation. Local requirements are to be followed for revised protocols.

AstraZeneca will distribute any subsequent amendments and new versions of the protocol to each Principal Investigator(s). For distribution to Ethics Committee see Section 8.3.

If a protocol amendment requires a change to a centre's Informed Consent Form, AstraZeneca and the centre's Ethics Committee are to approve the revised Informed Consent Form before the revised form is used.

If local regulations require, any administrative change will be communicated to or approved by each Ethics Committee.

## **8.6 Audits and inspections**

Authorised representatives of AstraZeneca, a regulatory authority, or an Ethics Committee may perform audits or inspections at the centre, including source data verification. The purpose of an audit or inspection is to systematically and independently examine all study-related activities and documents, to determine whether these activities were conducted, and data were recorded, analysed, and accurately reported according to the protocol, Good Clinical Practice (GCP), guidelines of the International Conference on Harmonisation (ICH), and any applicable regulatory requirements. The investigator will contact AstraZeneca immediately if contacted by a regulatory agency about an inspection at the centre.

## **9. STUDY MANAGEMENT BY ASTRAZENECA**

### **9.1 Pre-study activities**

Before the first patient is entered into the study, it is necessary for a representative of AstraZeneca to visit the ambulance organisation and the investigational study site to:

- Determine the adequacy of the facilities
- Determine availability of appropriate patients for the study
- Discuss with the investigator(s) (and other personnel involved with the study) their responsibilities with regard to protocol adherence, and the responsibilities of AstraZeneca or its representatives. This will be documented in a Clinical Study Agreement between AstraZeneca and the investigator.

In certain countries, the investigational study sites will involve the ambulance organisation and the hospital cardiology unit.

Prior to centre validation, a centre qualification process will take place. The independent Core Labs identified for the review and analysis of ECG and angiograms, will conduct a survey in order to check the quality of the documentation supporting the primary variables of the study and its transfer to the Core Lab. Preselected centers will have to submit at least 2 ECG recordings of the same patient with STEMI diagnosis. Recordings of two or more contiguous leads should be done in the pre-hospital and in-hospital (pre-PCI) setting and sent to Core lab along with the CD of the pre-PCI angiography imaging, for quality and variability assessment. The result of the survey will enable to confirm or not the centre participation to the study.

### **9.2 Training of study site personnel**

Before the first patient is entered into the study, an AstraZeneca representative will review and discuss the requirements of the Clinical Study Protocol and related documents with the investigational staff. The AstraZeneca representative will also train the site personnel in any study specific procedures and the WBDC system utilised (wherever it is appropriate).

The Principal Investigator will ensure that appropriate training relevant to the study is given to all of these staff, and that any new information relevant to the performance of this study is forwarded to the staff involved.

The Principal Investigator will maintain a record of all individuals involved in the study (medical, nursing and other staff).

### **9.3 Monitoring of the study**

During the study, an AstraZeneca representative will have regular contacts with the study site, including visits to:

- Provide information and support to the investigator(s)
- Confirm that facilities remain acceptable
- Confirm that the investigational team is adhering to the protocol, that data are being accurately and timely recorded in the eCRFs, ECGs and angiogram's for central review are handled in accordance with the Core Lab Manual and that study drug accountability checks are being performed
- Perform Source Data Verification (a comparison of the data in the eCRFs with the patient's medical records at the hospital and other records relevant to the study) including verification of informed consent(s) of participating patients. This will require direct access to all original records for each patient (eg, clinic charts)

The AstraZeneca representative will be available between visits if the investigator(s) or other staff at the centre needs information and advice about the study conduct.

#### **9.3.1 Source data**

Refer to the Clinical Study Agreement (CSA) for location of source data.

### **9.4 Study agreements**

The Principal Investigator at each centre should comply with all the terms, conditions, and obligations of the Clinical Study Agreement, or equivalent, for this study. In the event of any inconsistency between this Clinical Study Protocol and the Clinical Study Agreement, the terms of Clinical Study Protocol shall prevail with respect to the conduct of the study and the treatment of patients and in all other respects, not relating to study conduct or treatment of patients, the terms of the Clinical Study Agreement shall prevail.

Agreements between AstraZeneca and the Principal Investigator should be in place before any study-related procedures can take place, or patients are randomised.

#### **9.4.1 Archiving of study documents**

The Investigator follows the principles outlined in the Clinical Study Agreement (CSA).

### **9.5 Study timetable and end of study**

The end of the study is defined as 'the last visit of the last patient undergoing the study'.

The study is expected to start in     and to end by     .

The study may be terminated at individual centres if the study procedures are not being performed according to GCP, or if recruitment is slow. AstraZeneca may also terminate the entire study prematurely if concerns for safety arise within this study or in any other study with ticagrelor.

If AstraZeneca decides to prematurely terminate or suspend the study, the Principal Investigator, sub investigator, the head of the institution, and regulatory authorities should receive written notification of the reasons for the premature termination or suspension.

The Principal Investigator/sub-investigator will immediately notify the decision to the patients, give appropriate medical treatment; take necessary measures, and record treatment or measures provided on the source documents.

## **10. DATA MANAGEMENT**

Data management will be performed by staff and database set-up by the Data Management Centre of AstraZeneca.

Data queries will be raised for inconsistent, impossible or missing data and will be updated by the study site personnel as needed. All entries to the study database will be immediately saved to a central database and changes tracked to provide an audit trail

Data management will determine the format of the data to be collected through core laboratory and will produce ongoing reconciliation with clinical database as applicable.

Serious Adverse events Reconciliation reports will be produced and reconciled with Patient Safety database. Adverse events and medical/surgical history will be classified according to the terminology of the latest version the Medical Dictionary for Regulatory Activities (MedDRA). Medications will be classified according to the AstraZeneca Drug Dictionary. All coding will be performed by

All data will be validated as defined in the Data Management Plan. Quality control procedures will be applied to each stage of data handling to ensure that all data are reliable and have been processed correctly.

## **11. EVALUATION AND CALCULATION OF VARIABLES**

### **11.1 Calculation or derivation of efficacy variables**

ECG and angiographic assessments will be centrally measured.

The co-primary endpoint from ECG, complete ST –segment elevation resolution will evaluate the percentage of patients with an ST-segment elevation resolution  $\geq 70\%$  derived from percentage change in ST- segment elevation between ambulance assessment and in-hospital assessment pre-PCI.

The co-primary endpoint from angiography, TIMI flow grade 3 will evaluate the percentage of patients reaching TIMI flow grade 3 at initial angiography, issued from TIMI flow data, all grades.

Binary (yes/no) variables patients will be created and classified according to whether the specified event occurred.

Events related to secondary binary endpoints including complete ( $\geq 70\%$ ) ST-segment elevation resolution at 60 minutes post PCI, TIMI flow grade 3 at end of procedure, Thrombotic bail-out with GPIIb/IIIa inhibitors at initial PCI will be classified in the same way.

Length of time variables will be derived as the number of minutes from the onset to the end of the time interval considered. These intervals include time from symptom onset to first study medication administration and time from first study drug administration to time of ECG/angiography.

For the other endpoints, in each case patients will be classified (yes/no) according to whether one or more the events considered occurred during the 30 days of study. This includes the composite of death, MI, stroke, urgent revascularization, acute stent thrombosis and a similar composite including death, MI, and urgent revascularization.

Continuous variables measured by core lab include the correct TIMI frame count (cTFC) at angioplasty pre and post PCI and the ordinal TIMI myocardial perfusion grade (TMPG) at angioplasty pre and post PCI.

## **11.2 Calculation or derivation of safety variable(s)**

### **11.2.1 Bleeding Events**

Each patient will be classified (yes/no) according to whether there were one or more bleeding events according to the PLATO bleeding definition. This includes first, major life-threatening, second, other major bleeding events, and third, minor or major bleeding events. Two periods will be considered: the first 48 hours after first administration of study medication and during the 30 days of study. Thus each patient will have 6 classifications of “yes” or “no.”

### **11.2.2 Other significant adverse events (OAE)**

During the evaluation of the AE data, an AstraZeneca medically qualified expert will review the list of AEs that were not reported as SAEs and DAEs. Based on the expert’s judgement, significant adverse events of particular clinical importance may, after consultation with the Global Patient Safety Physician, be considered OAEs and reported as such in the Clinical Study Report. A similar review of laboratory, ECG and vital sign data will be performed for identification of OAEs.

Examples of these are marked haematological and other laboratory abnormalities, and certain events that lead to intervention (other than those already classified as serious), dose reduction or significant additional treatment.

## **12. STATISTICAL METHODS AND SAMPLE SIZE**

Statistical analyses will be performed by Statistic Department, using Statistical Analysis System (SAS). Statistical Analyses will be performed in accordance with the study protocol. The Statistical Analysis Plan will provide further details of the analyses and presentation of data. The statistical analysis plan will be finalised before the database lock.

### **12.1 Description of analysis sets**

#### **12.1.1 Efficacy analysis set**

The Modified Intent to Treat Population (mITT) will include all randomized patients who received a dose of study medication. Patients will be classified according to the treatment group they were randomized to. All efficacy endpoints will be analyzed using the mITT population.

#### **12.1.2 Safety analysis set**

All patients who received at least one dose of the study medical product will be included in the safety population. Throughout the safety results sections, erroneously treated patients (eg, those randomised to group A but actually treated as group B) will be accounted for in the actual treatment group. Patients who did not receive a dose of study medical product will not be considered.

### **12.2 Methods of statistical analyses**

Continuous variables will be summarized using mean, standard deviations and extreme values (minimum, maximum). Confidence intervals, when included, will be two-sided 95% intervals except otherwise specified. Categorical variables will be summarized in frequency tables including counts and percents. Values will be summarized by treatment group and overall.

#### **12.2.1 Primary Efficacy Endpoints**

Each of the co-primary endpoint will be analyzed separately using a Chi-Square test.

The Holm multiple correction procedure will be used to maintain an overall Type I error rate of 5%. Specifically the two derived p-values will be compared. If the smaller p-value is greater than 0.025 then neither null hypothesis is rejected. Alternatively, if it is less than 0.025 then the associated null hypothesis is rejected and the null hypothesis associated with larger p-value is rejected if the p-value is less than 0.05.

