### **5.2.1 Procedures for randomisation**

The randomization will occur at Visit 1 in pre-hospital settings after obtaining the Informed Consent. Visit 1 can be performed between 30 minutes and 6 hours of onset of symptoms of acute MI. Patients who satisfy all the eligibility requirements, will be randomised by the assignation of the randomisation number present on the treatment pack available. The first dose of investigational product will be administered to the patient immediately after opening the patient pack.

The randomization codes will be computer generated by AstraZeneca R&D using GRand (AZ Global Randomization system). A blocked randomization stratified by centre will be produced. The investigational product will be packed according to this randomization list.

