## **12.3 Determination of sample size**

Since, based on multiplicity procedure, the initial significance level is 2.5%, the sample size calculation will be based on a significance level of 2.5% and 80% power. Sample size calculations were derived using nQUERY7.

The sample size for the two co-primary endpoints is derived from the ST Resolution hypothesis. However, the study is enough powered for the 2 criteria when considering the table below.

The ST segment deviation was previously studied in On Time2 study (Van't Hof Aw et al 2008), where complete ST resolution occurred in 20.7% of patients in the pre-hospital GP I Ib/IIIa group versus 15.4% in the non GP I Ib/IIIa group, all patients receiving a clopidogrel loading dose. This last number, corresponding to an in-hospital group was confirmed in Assent 4 PCI study where electrocardiographic reperfusion was shown in 14.9% of patients.

Based on this data, it is hypothesized that 15% of patients in the in-hospital group will achieve complete ST elevation resolution versus 21% in the pre-hospital group (absolute difference of 6%). Taking into account a significance level of 2.5%, 779 evaluable patients are required in each treatment group to have 80% power using a two group chi squared test of equal proportions. Assuming a 12% dropout for invaluable or missing ECG criteria, a total of 1770 patients are required to be enrolled in the study to assess the ST segment elevation resolution difference.

To insure the sample size is adequate for the analysis of the co-primary endpoint TIMI Grade at initial angiography, values ranging from 15-27% were reported in various studies. Clinicians agreed that a 30 to 35% relative difference between the 2 groups is clinically relevant. In order to hypothesize on the various degree of angiographic reperfusion expected the following table was created to show a range of hypothesis and the related sample size. A statistical difference can be shown for the highlighted hypothesis (in bold) in the table. Dropout rate at initial angiography is assumed to be low, and less than 8%. These values indicate the sample size of 1770 patients is adequate for this endpoint.

	Assumptions with TIMI flow grade3 = 15% in in-hosp group		Assumptions with TIMI flow grade3 = 27% in in-hosp group	
Assumptions of relative difference (%) between the two groups	30	35	30	35
In-hosp group	15%	15%	27%	27%
Pre-hosp group	19.5%	20.3%	35.1%	36.5%
N per group with alpha=0.05	1106	826	512	376

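### Randomisation is stratified by centre, but the primary test of each co-primary is an unstratified chi-square: valid and powered as stated, yet it ignores the stratum and turns conservative if centres differ strongly

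*Protocol*

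**What the plan says.** Section 5.2.1 on allocation: "A blocked randomization stratified by centre will be produced". The synopsis plans about 120 centres in 10 to 15 countries and 1770 patients.

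Section 12.2.1 on the primary test: "Each of the co-primary endpoint will be analyzed separately using a Chi-Square test". It names no stratum and no covariate, and the synopsis gives the same test. Section 12.3 sizes the trial for that test: "779 evaluable patients are required in each treatment group to have 80% power using a two group chi squared test of equal proportions".

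Multiplicity is handled by Holm in section 12.2.1. First step: "If the smaller p-value is greater than 0.025 then neither null hypothesis is rejected". Once the first hypothesis has been rejected, "the null hypothesis associated with larger p-value is rejected if the p-value is less than 0.05".

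Section 12.2.1 sets no interval for the co-primaries. Section 12.2 has only a general default: "Confidence intervals, when included, will be two-sided 95% intervals except otherwise specified".

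The opening of section 12 says that the analyses will follow the protocol and that the statistical analysis plan will add detail.

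**The concern.** Blocking within centre removes centre differences from the comparison of the arms. The total variance of a binary outcome splits into a within-centre part and a between-centre part. The blocked design largely takes the second part out of the true variance of the treatment difference. The crude chi-square still charges for it, because its variance uses only the overall proportion. The more centres differ, the more the test overstates its own standard error.

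The protocol gives reasons to expect some difference. Section 5.6.3 leaves upstream GPIIb/IIIa use to the physician, section 1.4 acknowledges that pre-hospital antiplatelet practice varies, and many countries take part. At stake are a type I error below the level the plan sets and a modest amount of power.

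The test is written into the protocol. A statistical analysis plan that stratified the primary test would depart from section 12.2.1, so the change belongs in that section.

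The interval level is a smaller matter. A 95% interval reported by default can exclude zero when Holm's first step has rejected nothing.

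**Working it through.** **1. The plan's own figure.** Inputs from section 12.3: 15% against 21%, two-sided 2.5%, 80% power. The mean proportion is 0.18.

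n = [z(0.9875)·√(2·0.18·0.82) + z(0.80)·√(0.15·0.85 + 0.21·0.79)]² / 0.06²

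= [2.2414·√0.2952 + 0.8416·√0.2934]² / 0.0036

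= [1.2178 + 0.4559]² / 0.0036 = 778.1, rounded up to **779 per group**, as stated.

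Power at 779 per group is 80.05%. The total is 2·779 / 0.88 = 1770.5, so 1771 against the stated 1770. The planned test delivers what section 12.3 says.

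**2. Patients per centre.** 1770/120 is about 15 randomised, and 1558/120 is about 13 evaluable.

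**3. Crude chi-square against CMH by centre.** Simulation with 20,000 trials per setting, 1558 evaluable patients, 120 centres of unequal size, marginal rates of 15% and 21%, and two-sided 2.5%. Three inputs are assumptions that the protocol does not give: normal centre effects on the logit scale, their SD, and a block size of 4.

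| Assumed centre SD (logit) | Power, crude | Power, CMH | Change (points) | Type I error, crude | Type I error, CMH |
|---|---|---|---|---|---|
| 0 | 80.3% | 79.8% | -0.5 | 2.5% | 2.5% |
| 0.25 | 80.3% | 80.2% | -0.1 | 2.4% | 2.5% |
| 0.5 | 80.6% | 81.1% | +0.5 | 2.5% | 2.7% |
| 0.75 | 81.1% | 82.9% | +1.8 | 2.1% | 2.5% |
| 1.0 | 82.2% | 85.3% | +3.1 | 1.7% | 2.5% |

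A separate simulation with the same numbers of centres and patients and the same block size gave crude against CMH power of 80.4% and 79.9% at SD 0, 80.1% and 81.0% at SD 0.5, and 81.3% and 84.7% at SD 1.0. Its crude type I error was about 1.5 to 1.9% at SD 0.75 to 1.0. Together the two runs give the range of 1.5 to 2.1%.

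To read the SD: at a 15% rate the odds are 0.15/0.85 = 0.176. One SD either side multiplies or divides the odds by e^SD. At SD 0.5 (factor 1.65) that spans roughly 10% to 23%. At SD 1.0 (factor 2.72) it spans roughly 6% to 32%. The upper end of the table therefore means strong heterogeneity.

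**4. Intervals.** At the design effect the standard error is √(0.2934/779) = 0.0194.

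- At the design effect itself, the 95% interval is 6.0 ± 1.96·1.94 = 2.2 to 9.8 points and the 97.5% interval is 6.0 ± 2.241·1.94 = 1.7 to 10.3 points. Both exclude zero.
- With the same standard error, p = 0.03 corresponds to a difference of 2.170·1.94 = 4.2 points. The 95% interval is 0.4 to 8.0 and excludes zero. The 97.5% interval is -0.1 to 8.6 and includes it.

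So the 95% default and the 2.5% step disagree only when 0.025 < p < 0.05. For ST resolution at the design effect, that has probability 86.98% - 80.05% = 6.9%.

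**The case against.** The strongest reply is that nothing is broken. The crude test does not inflate type I error, the trial was sized for it, and it reaches 80%. That stands. A reader might infer that the plan wastes power, and the documents do not support this. Up to an SD of 0.5 the two tests are within about half a point to one point of each other, and with identical centres CMH is slightly worse. The larger gains need an SD for which the protocol gives no figure.

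Second, the conservatism depends on close balance within centre. Section 5.2 has packs held in ambulances and used from the lowest number available there, so blocks split across vehicles may stay incomplete. That stands as a caveat: looser balance would weaken the conservatism of the crude test.

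Third, on intervals, a reader might infer that the plan pairs a single 2.5% decision rule with 95% intervals. It does not. Section 12.2.1 prescribes no interval, the default in section 12.2 can be overridden, and Holm's second step is at 5%, where a 95% interval matches. Even with p between 0.025 and 0.05, Holm rejects if the other endpoint has already passed. Claims rest on p-values, so error control is unaffected.

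Fourth, a reader might infer that adjusting for time from symptom onset would add worthwhile power. The protocol gives no figure for the variance it explains, section 12.2.2 already relates it to each co-primary by logistic regression, and a supporting model would not change the power of the primary test.

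Nor would stratification repair TIMI flow at a 15% control rate. Section 12.3 asks for 1001 to 1339 per group there at 2.5%, against about 1770·0.92/2 = 814 available. That is a separate matter.

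**Conclusion.** The mismatch between design and analysis is real and is fixed in the protocol itself, but it is a modest improvement to make and not an error that threatens the trial. The planned chi-square is valid and meets its stated 80% power for ST resolution. It ignores the randomisation stratum and becomes conservative only if centres differ strongly: type I error of about 1.5 to 2.1% against 2.5% at an assumed SD of 0.75 to 1.0. Stratifying changes power by about -0.5 to +3 points over an assumed SD of 0 to 1.0. The case for changing rests on that asymmetry, a small worst loss against a larger possible gain, and on analysing the trial as it was randomised. The figures depend on the assumed centre SD, centre sizes and block size. The interval point is minor and concerns presentation only.

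**What to change.** In section 12.2.1, and in the matching synopsis text, make the primary test of each co-primary a CMH test stratified by centre. Pool small centres within country by a rule fixed before unblinding, since a centre with patients in only one arm contributes nothing to the test. Keep the unstratified chi-square as a sensitivity analysis. The Holm steps and the sample size stay as they are.

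As a minor addition, state that any interval reported for the co-primaries follows the Holm step in place of the section 12.2 default: 97.5% for the first hypothesis tested, and 95% for the second once the first is rejected.

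The cost is a wording change before unblinding, the work of writing the pooling rule, and about half a point of power if centres turn out to be alike. No patient procedure changes.
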